### **16.1.6. SUBGROUP ANALYSES OF KEY EFFICACY ENDPOINT**

Subgroup analyses will be performed for the key efficacy endpoint ESS, MWT, PGIc, CGIc for the age, gender, mean sleep latency time (minutes) on MWT as per each definition, and use of dopamine agonist at Baseline subgroups. For other key efficacy endpoints, subgroup analyses will be performed for age and gender only. (see Section 7.5) Subgroup having more than 10 subjects in each subcategory will be analyzed similarly to the key efficacy analysis while only descriptive statistics will be provided for subgroup having 10 or less than 10 subjects in any subcategory. Forest plot of the treatment difference in change from baseline to the end of the treatment period in ESS total score for each subgroup having more than 10 subjects will also be provided based on the mITT.

## **16.2. EXPLORATORY EFFICACY ENDPOINTS**

### **16.2.1. EXPLORATORY EFFICACY ENDPOINTS & DERIVATIONS**

Exploratory efficacy endpoints include the assessments described in the subsections below as measured by the observed and change from Baseline in scores to the end of the treatment period.

[figure not shown]
#### **16.2.1.1. MEAN SLEEP LATENCY TIME (IN MINUTES), AS DETERMINED BY THE MWT**

The MWT is the standard objective measure of an individual's ability to remain awake in a darkened, quiet environment and is commonly used to assess response to treatment. For subjects in Group 1 only, a 3-trial, 40-minute MWT will be performed (with an option to do a fourth trial) at Baseline and at Visits 3, 4, 5, and 6.

Each MWT during the study should be started at approximately the same time of the day. During the MWT trials, subjects should be seated in bed in a darkened room with the back and head supported by a bedrest (bolster pillow) such that their neck is not uncomfortably flexed or extended (Littner et al. 2005). Subjects will be instructed to sit still and remain awake for as long as possible during each of the three (or four) 40-minute trials separated by 2-hour intervals. The first MWT trial should occur approximately 1 hour after dosing with study drug at all visits at which the MWT will be conducted. If the subject falls asleep during a trial, they will be awakened and instructed to remain awake until the next trial. If the subject does not fall asleep, then the specific trial is terminated at 40 minutes and a sleep latency of 40 minutes is recorded. The subject is then instructed to remain awake (and will be awoken if they fall asleep) until the next trial.

For each trial, the following 3 different sleep latency time (in minutes) will be measured:

- The duration from light off to the first of three-consecutive sleep stage N1, or any sleep stage N2/N3/REM

- The duration from light off to the first epoch of any sleep stage (Stage N1, N2, N3 or REM)
- The duration from light off to the first 10-sec of continuous sleep

The mean sleep latency time (in minutes) for a specific visit will be calculated for each of the 3 types of sleep latency measurement. If there are at least three individual MWT trials with available sleep latency time, the mean of all available MWT trial sleep latency times measured during the specific visit will be used for calculating the mean sleep latency time on the MWT at that specific visit.

The mean sleep latency time computed by the central lab for each type of sleep latency measurements (mean of the first 3 MWT trials; if one of the first 3 MWT trials is not performed or if the result of one of the first three MWT trial cannot be determined during a specific visit, the mean sleep latency time on MWT will be reported as unknown for that specific visit) will not be used for the analysis, but will be reported in the subject data listing.

The following endpoint will be summarized:

[figure not shown]
- Observed and change from Baseline in the mean sleep latency time for each of the 3 types of sleep latency measurements, as defined above

#### **16.2.1.2. MDS-UPDRS PARTS III AND IV SCORES**

Movement Disorder Society-sponsored revision of the Unified Parkinson's Disease Rating Scale (MDS-UPDRS) is a 4-part clinical rating scale for patients with Parkinson's disease. Part III measures motor function by examination and Hoehn and Yahr staging, and Part IV measures dyskinesias, motor fluctuations, and "off dystonia". Subjects will complete the MDS-UPDRS Parts III and IV at Baseline and at Visits 3, 4, 5, and 6.

The following endpoints will be summarized:

- Observed and change from Baseline in MDS-UPDRS Part III total score, where the total score is the sum of all individual scores for the 33 items. If the scores of 8 or more items are missing, then the MDS-UPDRS Part III total score is not evaluable and will be set to missing. If the score of 7 or fewer items are missing, the MDS-UPDRS Part III total score will be equal to the mean of the non-missing scores multiplies by 33 and then, rounded to the integer (Goetz et al. 2015);
- Observed and change from Baseline in MDS-UPDRS Part IV total score, where the total score is the sum of all individual scores for items 4.1 to 4.6. If the score of 1 item is missing, then the MDS-UPDRS Part IV total score is not evaluable and will be set to missing (Goetz et al. 2015);
- Observed and change from Baseline in MDS-UPDRS Part IV *Dyskinesias* subcomponent score, where the subcomponent score is the sum of all individual scores for items 4.1 to 4.2. If the score of 1 item is missing, then the MDS-UPDRS Part IV *Dyskinesias* subcomponent score is not evaluable and will be set to missing (Goetz et al. 2015);
- Observed and change from Baseline in MDS-UPDRS Part IV *Motor fluctuations* subcomponent score, where the subcomponent score is the sum of all individual scores for items 4.3 to 4.5. If the score of 1 item is missing, then the MDS-UPDRS Part IV *Motor fluctuations* subcomponent score is not evaluable and will be set to missing (Goetz et al. 2015);
- Observed and change from Baseline in MDS-UPDRS Part IV *"Off" dystonia* subcomponent score, where the subcomponent score is individual score for item 4.6.

### 16.2.1.3. CGIc

The Clinician Global Impression of Change (CGIc) is a 7-point Likert-type rating scale. Investigators will rate their impression of any change from Baseline in the subject's condition on the scale ranging from 1 = very much improved to 7 = very much worse at Visits 3, 4, 5, and 6.

The following endpoints will be summarized:

- The CGIc in 7 categories;
- The CGIc dichotomized into two categories: improved (i.e., pooled of the 'very much improved', 'much improved' and 'minimally improved' categories) and not improved (i.e., pooled of the 'no change', 'minimally worse', 'much worse', and 'very much worse' categories).

### 16.2.1.4. PGIC

The Patient Global Impression of Change (PGIC) is a 7-point Likert-type rating scale. Subjects will rate the change from Baseline in their condition on the scale ranging from 1 = very much improved to 7 = very much worse at Visits 3, 4, 5, and 6.

The following endpoints will be summarized:

- The PGIC in 7 categories;
- The PGIC dichotomized into two categories: improved (i.e., pooled of the 'very much improved', 'much improved' and 'minimally improved' categories) and not improved (i.e., pooled of the 'no change', 'minimally worse', 'much worse', and 'very much worse' categories).

### 16.2.1.5. FSS

The Fatigue Severity Scale (FSS), a 7-point Likert-type rating scale. The scale consists of 9 items; the total score represents the mean score of each of the 9 items, yielding a score range between 1 and 7, with higher scores indicating a higher level of fatigue. If the score of 1 item is missing, then the FSS total score will be set to missing. Subjects will complete the FSS at Baseline and at Visits 3, 4, 5, and 6.

The observed and change from Baseline in FSS total score to the end of period will be summarized.

### 16.2.1.6. APATHY SCALE

The Apathy Scale assesses apathy in patients with PD and consists of 14 questions with four possible answers: items 1 to 8: Not at All (3), Slight (2), Some (1), A Lot (0); items 9 to 14: Not at All (0), Slight (1), Some (2), A Lot (3). The total score, ranging from 0 to 42, is obtained by summing the scores of the 14 items, with higher scores indicating more severe apathy. If the score of 1 question is missing, then the Apathy total score will be set to missing. Subjects will complete the Apathy Scale at Baseline and at Visits 3, 4, 5, and 6.

The following endpoints will be summarized:

- Observed and change from Baseline in Apathy total score
- Observed and change from Baseline in the first Apathy subscale score (i.e., cognitive-behavioral aspects of apathy, obtained by summing items 1, 2, and 4 to 8). If the score of 1 question is

missing, then the subscale score will be set to missing.

- Observed and change from Baseline in the second Apathy subscale score (i.e., general apathy, obtained by summing items 3, and 9 to 14). If the score of 1 question is missing, then the subscale score will be set to missing.

#### 16.2.1.7. SCOPA-cog

The Scales for Outcomes in Parkinson's disease-cognition (SCOPA-cog) evaluates the specific cognitive deficits in PD. The scale consists of 10 items with a total possible score of 43, with higher scores indicative of better cognition, total score being computed by summing the scores of the 10 items. If the score of 1 item is missing, then the total score will be set to missing. Subjects will complete the SCOPA-cog at the Screening, Baseline, and at Visits 3, 4, 5, and 6.

The following endpoints will be summarized:

- Observed and change from Baseline in SCOPA-cog total score
- Observed and change from Baseline in SCOPA-cog *Memory and learning* subscale score, where the subscale score is the sum of all individual scores for items 1 to 3 and 10. If the score of 1 item is missing, then the total score will be set to missing.
- Observed and change from Baseline in SCOPA-cog *Attention* subscale score, where the subscale score is the sum of all individual scores for items 4 and 5. If the score of 1 item is missing, then the total score will be set to missing.
- Observed and change from Baseline in SCOPA-cog *Executive functions* subscale score, where the subscale score is the sum of all individual scores for items 6 to 8. If the score of 1 item is missing, then the total score will be set to missing.
- Observed and change from Baseline in SCOPA-cog *Visuo-spatial functions* subscale score, where the subscale score is the individual score for item 9

### 16.2.2. MISSING DATA METHODS FOR EXPLORATORY EFFICACY ENDPOINTS

Missing exploratory efficacy endpoints will not be imputed.

### 16.2.3. ANALYSIS OF EXPLORATORY EFFICACY ENDPOINTS

#### 16.2.3.1. MEAN SLEEP LATENCY TIME (IN MINUTES), AS DETERMINED BY THE MWT

Each type of mean sleep latency time measurement as determined by the MWT will be summarized and analyzed similarly than the key efficacy endpoint (see Section 16.1.4). However, because the MWT will be optional and consequently result in a reduced sample size, there may be convergence issues associated with the mixed-effects model. In the event such issues arise, an analysis of covariance (ANCOVA) model without accounting for treatment sequence will be used at each visit.

### **16.2.3.2. CGIc AND PGIc**

Number and percentage of subjects in each CGIc/PGIc category will be provided.

Number and percentage of subjects who improved/did not improve as per the dichotomized CGIc/PGIc will also be provided and analyzed using a chi-square test to test the hypotheses of difference between placebo and each active dose. A histogram plot of the percentage of subjects reported as improved in CGIc/PGIc will be provided by treatment group.

### **16.2.3.3. MDS-UPDRS, FSS, APATHY SCALE, AND SCOPA-COG**

The observed and change from Baseline in scores for MDS-UPDRS, FSS, Apathy Scale, and SCOPA-cog will be summarized and analyzed similarly to the key efficacy endpoint (see Section 16.1.4). Additionally, for each total/subcomponent/subscale score, the number and percentage of subjects with a missing score value will be summarized by visit and treatment group.

A bar graphs of the LS Mean and SE in the change from baseline to the end of the treatment period will be presented for each total score by treatment group based on the mITT population.

### **16.2.4. SENSITIVITY TO EXPLORATORY EFFICACY ENDPOINTS**

For each type of mean sleep latency time on the MWT (refer to Section 16.2.1.1), MDS-UPDRS Part III total score (refer to Section 16.2.1.2), MDS-UPDRS Part IV total score (refer to Section 16.2.1.2), CGIc (refer to Section 16.2.1.3), PGIc (refer to Section 16.2.1.4), FSS total score (refer to Section 16.2.1.5), Apathy total score (refer to Section 16.2.1.6), and SCOPA-Cog total score (refer to Section 16.2.1.7), a sensitivity analysis to the analysis population based on the PP will be performed.

[figure not shown]
An additional sensitivity analysis will be performed for each type of mean sleep latency time on the MWT to assess the impact of the truncated nap period. For this sensitivity analysis, unknown value (UNK) of individual MWT result with MWT trial length = 39.5 will be imputed by the trial length.

[figure not shown]
No sensitivity analysis will be performed for any subscale score and for any other exploratory efficacy endpoints.

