## 7.2. MISSING DATA

Missing or partially missing concomitant medication and adverse event (AE) start and stop dates will be imputed as described in APPENDIX 1. However, imputed dates will NOT be presented in the listings, as their sole purpose will be for the classification of the medications as prior, concomitant, or post-treatment (refer to Section 13) and the classification of AEs as prior, treatment-emergent, or post-treatment (refer to Section 17.1.1).

Missing data for ESS total score will be imputed as specified in Section 16.1.1 and missing data for the Movement Disorders Society-Unified Parkinson's Disease Rating Scale (MDS-UPDRS) Parts III total score will be imputed as specified in Section 16.2.1.2.

All other missing data will not be imputed.

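### MWT trials scored unknown at 39.5 minutes are left out of the main analysis and imputed only in a sensitivity analysis, so near-ceiling results are lost because of the outcome

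*SAP*

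**What the plan says.** SAP 16.2.1.1 defines how a completed trial is scored: "If the subject does not fall asleep, then the specific trial is terminated at 40 minutes and a sleep latency of 40 minutes is recorded". Group 1 has three trials per visit, and a fourth is optional. A visit mean is calculated "If there are at least three individual MWT trials with available sleep latency time", and then "the mean of all available MWT trial sleep latency times measured during the specific visit will be used". The rule is applied to each of three definitions of sleep latency.

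Two sections close off imputation for the MWT. After the provisions for dates, ESS and MDS-UPDRS Part III, SAP 7.2 states: "All other missing data will not be imputed". SAP 16.2.2 states: "Missing exploratory efficacy endpoints will not be imputed".

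The only exception is in SAP 16.2.4. To examine the effect of truncated trials, an additional sensitivity analysis provides that an "unknown value (UNK) of individual MWT result with MWT trial length = 39.5 will be imputed by the trial length". The SAP does not say how many trials ended at 39.5 minutes, and it has no rule for any other truncated length.

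**The concern.** Together these sections treat two almost identical results very differently. A subject still awake at 40 minutes gets the best possible score. A subject whose recording ends half a minute earlier with an unknown result contributes nothing to the main visit mean. A truncated trial in which sleep came sooner has a known latency and is kept, so the loss falls on the good outcomes.

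Three trials are standard and three are required, so one such trial normally removes the whole visit. The MWT is optional and SAP 16.2.3.1 already expects a reduced sample. The mixed model can make up for lost visits only if they are missing at random, and these are missing because of the outcome. The fallback, a separate ANCOVA at each visit, borrows nothing from a subject's other visits.

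SAP 16.2.4 does not extend the imputation to the MWT subgroup analyses and forest plots (16.2.5) or to the correlations and scatter plots (16.3). Those outputs would all rest on the version with the losses.

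**Working it through.** **Inputs.** The score of 40, the three-trial minimum and the averaging rule are from SAP 16.2.1.1. The bar on imputation is from 7.2 and 16.2.2, and the value 39.5 from 16.2.4. All individual trial values and simulation settings below are assumptions. The plan gives no figure on this point to reproduce: its only power figure, 80%, is for ESS and has no bearing here.

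**Step 1: which results are lost.** If qualifying onset occurs before 39.5 minutes, the latency is known. An unknown result to which the plan is willing to assign the trial length must be one with no qualifying onset by then. On a scale capped at 40, its score would have been between 39.5 and 40.

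**Step 2: effect on one visit.**

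- Three trials (UNK, 25, 22). Main analysis: two available trials, fewer than three, so the visit is missing. With imputation: (39.5 + 25 + 22)/3 = 28.8 minutes.
- Four trials (UNK, 25, 22, 20). Main analysis: (25 + 22 + 20)/3 = 22.3. With imputation: (39.5 + 25 + 22 + 20)/4 = 26.6. The main analysis is 4.3 minutes lower.
- In general, if the other three trials average m, main minus imputed is m − (3m + 39.5)/4 = (m − 39.5)/4. This is negative whenever m is below 39.5. If the other three are all 40 it is +0.125, so the downward shift is usual but not universal.

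**Step 3: effect on average latency.** A simulation used 200,000 visits per scenario. Latent mean latency was 15 to 30 minutes, between- and within-subject SD were each 10, and scores were capped at 40. A fraction q of trials without sleep by 39.5 minutes became UNK. The table gives the error in the average of the visit means that can still be calculated.

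| Trials | Latent mean | q | Error, UNK dropped (min) | Visits lost |
|---|---|---|---|---|
| 3 | 15 | 5% | −0.10 | 0.6% |
| 3 | 20 | 10% | −0.35 | 2.5% |
| 3 | 30 | 50% | −3.13 | 29.4% |
| 4 | 15 | 5% | −0.03 | 0.0% |
| 4 | 20 | 10% | −0.10 | 0.1% |
| 4 | 30 | 50% | −1.85 | 11.7% |

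The error was downward in every scenario. With 39.5 imputed it was never larger than about 0.06 minute.

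**Step 4: effect on a treatment difference.** Latent means were 28 and 20, q was equal in both groups, and nothing was truncated at Baseline. The true difference is about 6.5 minutes. With UNK dropped it becomes 6.3, 5.9 and 5.3 for q = 10%, 25% and 50% with three trials, and 6.4, 6.2 and 5.7 with four. These are differences of simple averages, not mixed-model estimates.

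**Step 5: Baseline.** The analysed variable is change from Baseline, with the Baseline value as covariate, and the same averaging rule applies at Baseline. If the four-trial example occurred there, Baseline would be 22.3 instead of 26.6 and each of the subject's change scores would rise by 4.3. If a three-trial Baseline visit is lost, the subject has no change scores unless a repeat test before first dose supplies a value. Steps 3 and 4 do not cover this.

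**The case against.** The best counter-argument is that the plan has already seen the problem. SAP 16.2.4 prespecifies the imputation for all three latency definitions, the MWT is exploratory, there is no multiplicity scheme, and no decision depends on which version is called the main one. The mixed model also keeps a subject's other periods when one post-Baseline visit is lost. All of this stands, and it limits the importance of the point. It does not explain why the version with outcome-dependent loss should lead, or why the subgroup and correlation outputs should rest on it.

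Some stronger conclusions are tempting but not supported:

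- A reader might take the SAP to state that no sleep occurred in these trials. It does not; that is inferred from the choice of imputed value. SAP 16.2.1.1 also uses unknown, for the central laboratory's visit mean, where a trial was not done or its result could not be determined. Under the definition that needs a run of N1 epochs, a trial cut off during such a run might be undeterminable although the subject was not fully awake. The missing value would probably still be high.
- A reader might infer that the treatment contrast is necessarily biased toward no effect. Truncation at Baseline can raise change scores or remove them, so the direction is not fixed. High Baseline latencies are plausible: MWT was removed as an eligibility criterion in Amendment 2 (Protocol 9.12), and SAP 7.5 plans a Baseline subgroup at 30 minutes or more.
- A reader might set the 4.3-minute example against the 8.1 to 11.8 minute narcolepsy effects in Protocol 1.1. The first is the error in one hypothetical visit; the others are mean differences between treatments. They are not comparable.
- Imputing 39.5 is not strictly unbiased, since it can understate the score slightly.

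**Conclusion.** The concern holds for the way the main visit mean is built. A trial of 39.5 minutes with an unknown result is unavailable, deletes a three-trial visit, and at a four-trial visit lowers the mean unless the other trials average 39.5 or more. The loss depends on the outcome and generally biases mean latency levels downward. This rests on the inference that such trials showed no qualifying onset, which the plan's own imputation strongly implies.

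For the treatment contrast, attenuation is the expected direction only if no-sleep trials are commoner on active drug and truncation at Baseline does not offset it. The overall size cannot be determined because the frequency of 39.5-minute trials is not given. Under the assumed settings it ranges from negligible to about 3 minutes in mean level, and from about 0.1 to 1.2 minutes in a 6.5-minute contrast. For an exploratory endpoint with a planned sensitivity analysis, this is of modest importance, but worth correcting because the correction is cheap.

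**What to change.** In SAP 16.2.1.1, set UNK results with trial length 39.5 minutes to 39.5 in the main MWT analysis, at Baseline and at all post-Baseline visits, for all three latency definitions. Add a matching exception to 7.2 and 16.2.2. State that the same derived values feed the MWT subgroup outputs (7.5, 16.2.5) and the correlations and plots (16.3). In 16.2.4, make the version that leaves these results missing the sensitivity analysis.

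The cost is a change of SAP wording; both versions are already specified, and no new data are needed. The downside is an understatement of at most 0.5 minute per imputed trial, which is at most 0.5/3 = 0.17 minute in a three-trial visit mean with one such trial.

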### **16.2.5. SUBGROUP ANALYSES OF EXPLORATORY EFFICACY ENDPOINT**

Subgroup analyses for each type of mean sleep latency measurement as determined by the MWT, MDS-UPDRS Part III total score, MDS-UPDRS Part IV total score, Apathy Total Score, FSS total score, SCOPA-Cog total score, CGIc, and PGIc will be performed for the age, gender, ESS total score, and use of dopamine agonist at Baseline subgroups (refer to Section 7.5). Subgroup having 10 subjects or more will be analyzed similarly to the primary analysis of the key efficacy endpoint while only descriptive statistics will be provided for subgroup having less than 10 subjects. Forest plot of the treatment difference in change from baseline to the end of the treatment period for each type of mean sleep latency measurement as determined by the MWT will also be provided based on the mITT for each subgroup having more than 10 subjects.

Subgroup analyses will not be performed for any subscale score and for any other exploratory efficacy endpoints.

